8.3.2 CLASSIFICATION OF AN ADVERSE EVENT

8.3.2.1 SEVERITY OF EVENT

For adverse events (AEs) not included in the protocol defined grading system, the following guidelines will be used to describe severity.

- **Mild** – Events require minimal or no treatment and do not interfere with the participant's daily activities. (Equivalent to Grade 1 events if using CTCAE reporting)
- **Moderate** – Events result in a low level of inconvenience or concern with the therapeutic measures. Moderate events may cause some interference with functioning. (Equivalent to Grade 2 and 3 events if using CTCAE reporting)
- **Severe** – Events interrupt a participant's usual daily activity and may require systemic drug therapy or other treatment. Severe events are usually potentially life-threatening or incapacitating. Of note, the term "severe" does not necessarily equate to "serious". (Equivalent to Grade 4 events if using CTCAE reporting)

8.3.2.2 RELATIONSHIP TO STUDY PROCEDURE

All adverse events (AEs) must have their relationship to investigational device and/or procedure assessed by the clinician who examines and evaluates the participant based on temporal relationship and his/her clinical judgment. The degree of certainty about causality will be graded using the categories below. In a clinical trial, the study product must always be suspect.

- **Definitely Related** – There is clear evidence to suggest a causal relationship, and other possible contributing factors can be ruled out. The clinical event, including an abnormal laboratory test result, occurs in a plausible time relationship to study intervention administration and cannot be explained by concurrent disease or other drugs or chemicals.
- **Probably Related** – There is evidence to suggest a causal relationship, and the influence of other factors is unlikely. The clinical event, including an abnormal laboratory test result, occurs within a reasonable time after administration of the study intervention, is unlikely to be attributed to concurrent disease or other drugs or chemicals.
- **Possibly Related** – There is some evidence to suggest a causal relationship (e.g., the event occurred within a reasonable time after administration of the investigational device and/or procedure). However, other factors may have contributed to the event (e.g., the participant's clinical condition, other concomitant events). Although an AE may rate only as "possibly related" soon after discovery, it can be flagged as requiring more information and later be upgraded to "probably related" or "definitely related", as appropriate.
- **Not Related** – The AE is completely independent of study intervention administration, and/or evidence exists that the event is definitely related to another etiology. There must be an alternative, definitive etiology documented by the clinician.]

An AE becomes an ADE when the AE is considered if the attribution is possibly, probably or definitely related associated with the use of the test device.

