All procedure images and reports, regardless of the randomization arm, will be kept with the unblinded member of the study team, and will not be housed centrally. All participants will adhere to the same follow-up schedule, meeting with blinded members of the study team only. The procedural team will not have further contact with the participant, the participant will only be followed by the blinded study team. Once the study is closed, all reports and images will be entered into the clinical record.

Bariatric Embolization Procedure

The bariatric embolization procedure will be performed under moderate sedation by experienced interventional radiologists. This procedure will take about one-and-a-half to three hours. The manufacturer's Instruction for Use will be followed for the procedure.

The participant will be placed on the X-ray fluoroscopy table. Radial or femoral vascular access will be achieved using a small 21-gauge needle, then dilated serially over a guidewire to accommodate a 5 French vascular sheath(23). The participant will receive local anesthesia in the skin of their leg or wrist, then a different small catheter will be placed through the participant's skin into an artery that leads to the participant's abdomen.

Using standard catheters, 3-dimensional imaging will be acquired of the stomach, the arteries supplying the fundus arising off the celiac vessel will be selected. Then, a microcatheter will be advanced into the left gastric and/or gastroepiploic arteries supplying the fundus and small calibrated spheres (100-200 μm size [BTG-001933]) will be infused until stasis of anterograde arterial flow is achieved, with particular care to avoid infusion of non-target arteries. Only the left gastric and/or gastroepiploic arteries will be embolized. Stasis will be defined as visualization of contrast within the target artery for at least 5 cardiac cycles.

Upon completion, repeat 3-dimensional imaging will be acquired to assess bead distribution and fundal coverage. Following this the catheters will be removed and hemostasis will be achieved with manual compression or a closure device.

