8.3 ADVERSE EVENTS AND SERIOUS ADVERSE EVENTS

Definition of Adverse Events (AE) and Adverse Device Effects (ADE)

Adverse event (AE) means any untoward medical occurrence, unintended disease or injury, or untoward clinical signs (including abnormal laboratory findings) in subjects, users, or other persons, whether or not related to the investigational medical device.

An adverse device effect (ADE) is an AE, as previously defined, related to the use of an investigational medical device. This includes any adverse event resulting from insufficiencies or inadequacies in the instructions for use, the deployment, the implantation, the installation, the operation, or any malfunction of the investigational device. This includes any event that is a result of a use error or intentional abnormal use of the investigational medical device.

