9.4.6 PLANNED INTERIM ANALYSES

An interim analysis of safety and technical utility of the embolic device (image visibility) and procedural assessments such as blinding, will be done after the 10 pilot patients complete the embolization procedure. Study reports on device/ procedure related complications are to be sent to the FDA following treatment of the ten (10) pilot patients and then after every 10 additional subjects are randomized and treated (blinded).

No interim analysis for efficacy or futility are planned.

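### The causality scale has no category for an unexplained AE, so such events are likely to be recorded as adverse device effects, possibly in sham participants too

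*Protocol*

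**What the plan says.** Protocol section 8.3.2.2 makes causality grading compulsory: "All adverse events (AEs) must have their relationship to investigational device and/or procedure assessed by the clinician who examines and evaluates the participant". It adds: "The degree of certainty about causality will be graded using the categories below". The levels are Definitely, Probably, Possibly and Not Related. Possibly Related begins: "There is some evidence to suggest a causal relationship (e.g., the event occurred within a reasonable time after administration"; other contributing factors may also be present. Not Related opens by offering complete independence from the intervention and/or proof of a different cause. It then adds: "There must be an alternative, definitive etiology documented by the clinician". The introduction to the scale states: "In a clinical trial, the study product must always be suspect". The section closes by making an AE an ADE once it is graded possibly related or higher in association with use of the test device.

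Section 8.3 gives the governing definition: "An adverse device effect (ADE) is an AE, as previously defined, related to the use of an investigational medical device". Under section 6.1.1, sham participants have a simulated procedure with local anaesthetic and a skin nick, and no embolization. Both arms are then followed on the same schedule, "meeting with blinded members of the study team only".

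Section 9.4.6 says: "Study reports on device/ procedure related complications are to be sent to the FDA". The reports fall due after the ten pilot patients and after each further ten randomized and treated. Section 10.1.6 sends the same reports to the DSMB.

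**The concern.** A causality scale applied to every AE should have a place for every AE. In a 12-month obesity trial some events will have no particular link to the procedure and no proven cause, such as a headache or back pain at month 5. If these have no proper home, their grade depends on how each clinician resolves the gap, and the instruction to suspect the product pushes towards a related grade.

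Two features add to this. One grade covers device and procedure together, so an access-site event cannot be told apart from a bead event by its grade. The grader at follow-up is also blinded, and so cannot apply a definition that turns on whether a device was used. What is at stake is the ADE, SADE and UADE listing for an investigational embolic, and the periodic complication reports that rest on relatedness.

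**Working it through.** No arithmetic applies and the plan states no figure on this point. The check sets the definitions side by side.

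**Step 1: is the scale exhaustive?** Cross the two conditions used in section 8.3.2.2.

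| Evidence of a link | Definitive other cause documented | Level that fits |
|---|---|---|
| Yes | No | Possibly, Probably or Definitely Related, by strength |
| Yes | Yes | Possibly Related and Not Related can both be argued |
| No | Yes | Not Related |
| No | No | None |

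In the last row, Possibly Related fails because it needs some evidence, and Not Related fails because no definitive cause is documented. The and/or in the first sentence of Not Related seems to let complete independence suffice, but the sentence after it makes a documented cause mandatory and closes that route.

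**Step 2: which events fall in the last row?** Timing alone is given as an example of evidence for Possibly Related, so events soon after the procedure can enter that level legitimately. The gap is mainly later events of unclear cause.

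**Step 3: where do they go?** Read literally, they cannot be graded. In practice a grade is compulsory, Not Related is barred without a proven cause, and the product is to be suspected. Possibly Related is the likely choice, and it is enough for an ADE under the closing sentence of the section. This step is an inference about behaviour, not a written rule.

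**Step 4: the sham arm.** Sections 8.3 and 8.3.2.2 both tie an ADE to use of the device. Sham participants receive none, so by definition they cannot have an ADE. But section 8.3.2.2 gives the grading to the examining clinician, and section 6.1.1 makes that a blinded person during follow-up. That person grades device and/or procedure on one scale. A sham event can therefore be entered as possibly related and carried as an ADE until unblinding. Neither document says how ADE status is settled for sham participants. The pilot patients are all embolized, so for them only the gap in Step 1 arises.

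**Step 5: which outputs use the grade?**

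- Affected: ADE, SADE and UADE status (sections 8.3 to 8.3.2.3), the reporting that follows from it (section 8.3.5), and the complication reports (sections 9.4.6 and 10.1.6).
- Not affected: the 12-month and 30-day safety outcomes in protocol section 9.4.4 and SAP sections 3.5 and 5.4, which count AEs without restriction by relatedness. Section 8.3.3 requires AEs to be documented whatever their relationship.

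**The case against.** The strongest reply is that little depends on this. No planned analysis uses ADE counts. The randomized comparison of all AEs needs no attribution, and the DSMB sees safety data by arm. Any error is towards over-attribution, which is the cautious direction. All of that stands, and it limits the point to classification and reporting.

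A second reply is that combined attribution is deliberate. Section 8.3 counts events arising from deployment and operation of the device as ADEs. Section 8.3.1 brings unanticipated procedure-related serious events into its unanticipated category. Section 8.3.2.3 judges expectedness against device and/or procedure risk, and the FDA reports cover both. This has force: a combined field suits those reports. It does not supply the narrower device-related judgement that the ADE definition asks for.

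Three stronger readings are tempting, and the documents do not support them:

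- *Unexplained AEs default to ADEs by rule.* No default is written; the literal result is an event that cannot be graded.
- *Sham events are ADEs under the protocol.* The definition excludes them; they can only be mislabelled.
- *The trial could not show whether the beads cause harm.* The all-AE comparison between arms is untouched.

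A reader might also try to size the effect from the omeprazole side-effect percentages in section 2.3.1. Those events have a candidate cause, the drug, so they do not measure AEs without one.

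**Conclusion.** The concern holds in a limited form. The gap in the scale follows directly from the text of section 8.3.2.2. That unexplained events will tend to be graded possibly related, and so become ADEs, is a reasonable inference from compulsory grading and the presumption against the product. That some will be in sham participants follows if blinded follow-up staff do the grading, as sections 6.1.1 and 8.3.2.2 together imply.

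No numerical size can be given: neither document states how many AEs per participant would lack a proven cause, or how clinicians would grade them. This is a classification defect worth correcting. It does not threaten the primary efficacy analysis or either planned safety comparison.

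**What to change.** In section 8.3.2.2 and on the AE eCRF:

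1. Add an Unlikely Related level, defined as no reasonable evidence of a causal link and no definitive alternative cause, and state that it does not count as an ADE. Alternatively, delete the mandatory-etiology sentence from Not Related. The added level is cleaner, because complete independence would remain a demanding standard for an unexplained event.
2. Record relationship to the device and relationship to the procedure in separate fields.
3. Keep blinded grading and expedited reporting identical in both arms. Restrict the final ADE, SADE and UADE tabulation to participants who received beads, either at unblinding or through the existing unblinded role in a file that blinded staff cannot see.

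The third item needs this form. If ADE status were assigned during follow-up only to bead recipients and shown on the eCRF or in a report, the label itself would reveal the arm.

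The cost is one response option, one extra field, protocol wording and, if the unblinded role is used, a restricted file. Attribution becomes slightly less conservative. Every AE is still recorded and counted.

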8.3.2.3 EXPECTEDNESS

The investigator will be responsible for determining whether an AE is expected or unexpected based on the device labelling and Investigator Brochure. An AE will be considered an unanticipated adverse device effect (UADE) if the nature, severity, or frequency of the event is not consistent with the risk information previously described for the investigational device and/or procedure.

8.3.3 TIME PERIOD AND FREQUENCY FOR EVENT ASSESSMENT AND FOLLOW-UP

The occurrence of an adverse event (AE) or serious adverse event (SAE) may come to the attention of study personnel during study visits and interviews of a study participant presenting for medical care, or upon review by a study monitor. In this study, patients should be encouraged to report AEs spontaneously or in response to general, non-directed questions.

All AEs including local and systemic reactions not meeting the criteria for SAEs will be captured on the appropriate case report form (CRF). Information to be collected includes event

description, time of onset, clinician's assessment of severity, relationship to investigational device and/or procedure (assessed only by those with the training and authority to make a diagnosis), and date and time of outcome of the event. All AEs occurring while on study must be documented appropriately regardless of relationship. All AEs will be followed to adequate resolution or stability.

Any medical condition that is present at the time that the participant is screened will be considered as baseline and not reported as an AE. However, if the study participant's condition deteriorates at any time during the study, it will be recorded as an AE.

Changes in the severity of an AE will be documented to allow an assessment of the duration of the event at each level of severity to be performed. AEs characterized as intermittent require documentation of onset and duration of each episode.

The investigator or designee will record all reportable AEs (includes AE, ADE, SAE, SADE, UADE) with start dates occurring any time after exposure to the investigational device. An AE occurring after informed consent and prior to exposure of the investigational device will be added to the subject's history. All AEs will be collected through the last day of study participation. At each study visit, the investigator will inquire about the occurrence of AE/SAEs since the last visit. Events will be followed for outcome information until resolution or stabilization.

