6 STUDY INTERVENTION

6.1 STUDY INTERVENTION(S) ADMINISTRATION

6.1.1 STUDY INTERVENTION DESCRIPTION

This study is being conducted under IDE G190208 utilizing an investigational device, BTG-001933, which is a radiopaque embolic bead 100-200 µm (Biocompatibles UK, Ltd) intended to be used for bariatric embolization [of the left gastric and/or gastroepiploic arteries](#). The summary of test validation studies is on file with the FDA and available in the Investigator's Brochure.

Control Arm Procedures

Participants randomized to the control arm will follow the same screening and pre-procedure assessment, and will also take the same pre-procedure medications. After becoming eligible, participants will be scheduled for their procedure. On procedure day, the interventional radiologist will determine radial or groin access in the post-anesthesia care unit per local policy. After the participant and procedure area are prepped, and a basic tray is opened, all participants will be given standard moderate sedation medications. At this point, the participant will have a drape placed over a drape support above their face to limit their vision and be given ear plugs and noise-cancelling headphones to dampen their hearing, preventing them from seeing and hearing the procedure but still allowing them to keep in contact with the procedure team. The participant will be randomized to either the control or intervention arm using central randomization software. Participants randomized to the control arm will receive no other procedural intervention. The procedural team instead will follow a prescribed simulated protocol that will mimic an actual embolization procedure. All participants will receive subcutaneous lidocaine and a skin nick to their groin or their wrist as pre-determined by the operating physician in the pre-anesthesia care unit, including those randomized to the control arm. If the skin nick is on the wrist, the operating physician will close it with an external compression device, and if it is in the groin, the physician will hold pressure for at least 5 minutes.

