8.3.4 ADVERSE EFFECT REPORTING

Adverse events will be recorded on the AE eCRF. The Investigator or physician sub-Investigator will judge the severity of each AE and whether or not it is treatment-related. All AEs that occur after signing of informed consent including events likely to be related to the underlying disease or likely to represent concurrent illness, will be reported, including events present at Baseline which worsened during the study.

The Investigator will be responsible for informing the IRB and reporting annually to the FDA as outlined in 21 CFR 812.

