9.4.4 SAFETY ANALYSES

The primary safety endpoint will be the differences in adverse events at 12 months post procedure. The statistical analysis on the secondary outcome for safety will consider differences in the adverse events (AEs) at 30-days post-procedure.

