3.5 Outcome Measures

Primary Efficacy Endpoint

The primary outcome is the change in body weight at 12 months' post-procedure from baseline weight.

Secondary Efficacy Endpoints

Secondary efficacy endpoints include the following: 1) Percent change in body weight at 12 months' post-procedure from baseline; 2) The achievement of > 5% reduction in body weight at 12 months' post-procedure; 3) Percent excessive weight loss (EWL) at 12 months' post-procedure from baseline; and 4) Change in MRI biomarkers liver fat proton

density fat fraction (PDFF), visceral adipose tissue volume, subcutaneous adipose tissue volume, and muscle fat infiltration.

Primary Safety Outcome

The total adverse events (AEs) from procedure to 12 months' post-procedure will be used to assess the safety of the BAE procedure and the use of radiopaque 100-200 μm microspheres in obese patients.

Secondary Safety Outcome

The total number of events until day 30 post-procedure will be considered the secondary safety outcome.

Exploratory Outcomes

The following outcomes will be considered as exploratory and potentially supportive of future research studies: 1) Change in blood pressure; 2) Change in lipid/lipoprotein profiles; 3) Change in obesity related hormones (ghrelin, LEAP2, leptin, glucagon-like peptide-1, peptide YY, etc.); 4) Changes in markers of obesity-related complications; 5) Food intake; 6) Hungry and satiety measures; 7) Quality of life as measured by the SF-36 and IWQOL; 8) Endoscopy results; 9) Ghrelin expression in pre- and post-operative fundal biopsy samples; 10) Changes in taste perception; 11) Image analyses of bead distribution and fundal coverage; 12) Embolization endpoints of occlusion and recanalization; 13) Change in muscle volume; 14) Change in muscle fat infiltration; 15) Change in visceral adipose tissue; 16) Change in CHD propensity; 17) Change in DT2 propensity; and 18) Differing treatment response in patients with adverse muscle composition.

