4.2 Safety Analysis Set

Patients in the Safety Analysis Set (SAS) will include all individuals who are randomized and who underwent the procedure to which they were assigned. Patients in the SAS may include those individuals who do not complete any post-procedure, follow-up visits (i.e. have no post-procedure outcome measures). In addition, patients in the safety data set may include patients who underwent partial embolization or partial sham procedure due to the procedure being stopped short for any reason.

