5.4 Analysis of the Safety Measures

The primary safety endpoint will be the differences in adverse events at 12-months post procedure. The statistical analysis on the secondary outcome for safety will consider differences in the adverse events (AEs) at 30-days post-procedure.

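### Protocol 8.3.3 starts adverse-event recording at device exposure, so as written the two arms do not share one recording window for the primary and secondary safety comparisons

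*Protocol*

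**What the plan says.** Protocol 8.3.3 tells the investigator to record all reportable events "with start dates occurring any time after exposure to the investigational device". It continues: "An AE occurring after informed consent and prior to exposure of the investigational device will be added to the" history of that subject. Section 6.1.1 identifies the device as the BTG-001933 bead and says of the sham arm: "Participants randomized to the control arm will receive no other procedural intervention". Sham participants do get lidocaine and a skin nick, but no beads.

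Three other places give a different start:
- Protocol 8.3.4 reports "All AEs that occur after signing of informed consent".
- SAP 3.5 defines the primary safety outcome as "The total adverse events (AEs) from procedure to 12 months" after it.
- The endpoint table in protocol section 3 counts 12 months from randomization.

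These events feed the designated safety comparisons. SAP 5.4 states: "The primary safety endpoint will be the differences in adverse events at 12-months post procedure". Protocol 9.4.4 says the same, and both add a secondary comparison at 30 days. SAP 4.2 keeps in the safety set "patients who underwent partial embolization or partial sham procedure due to the procedure being stopped short for any reason".

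**The concern.** A between-arm comparison of adverse events is interpretable only if events are looked for and recorded over the same period in both arms. Section 8.3.3 opens the period with something that one arm receives and the other does not. In the embolization arm it opens the period late, after arterial access and catheter work. An embolization stopped before any bead was given could stay in the safety set and yet have no event that the rule allows to be recorded.

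The direction of any distortion is not fixed. If sham procedure-day events are filed as history while events after bead infusion are counted, harm from the device looks larger than it is. If sham events are counted from the skin nick while pre-bead events in the embolization arm go to history, harm from the procedure looks smaller than it is. The SAP counting window cannot repair either case, because an event filed as history is not on the adverse-event form to be counted.

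**Working it through.** **Start points side by side**

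| Source | Window opens at | Sham arm | Embolization arm |
|---|---|---|---|
| Protocol 8.3.3 | Device exposure | Never opens | Bead infusion |
| Protocol 8.3.4 | Consent | About two months before the procedure (8.1) | Same |
| SAP 3.5 | Procedure | Procedure day | Same |
| Protocol section 3 | Randomization | Procedure day (1.3, 6.1.1) | Same |

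Only the first row differs by arm. No text reconciles the rows or defines a sham equivalent of exposure.

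**Order of events on procedure day (protocol 6.1.1).** Sedation, then drape and headphones, then randomization, then lidocaine and skin nick in both arms. In the embolization arm, arterial access, catheter placement, imaging and bead infusion follow. Under 8.3.3 everything between randomization and the beads is left out in the embolization arm. Several risks named in protocol 2.3.1 can begin in that interval: access-site bleeding, contrast reaction, vessel perforation and vasospasm.

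**Group size.** The plan states no adverse-event figure, so the only figure to reproduce is the group size. Inputs from protocol 9.2: difference 8 − 3.3 = 4.7 kg, SD 7 kg, two-sided alpha 0.20, power 80%.
- Normal approximation: n = 2 × (1.2816 + 0.8416)² × (7/4.7)² = 20 per arm.
- Exact t: power is 79.4% at 20 and 80.9% at 21, so the plan's 21 reproduces.
- Dropout: 21/0.8 = 26.25, rounded up to 27 per arm, as stated.

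**Events before bead infusion.** The documents give no rate, so I assume a share p of embolization participants with such an event, independent between participants. Expected number uncounted = 27p; chance of at least one = 1 − (1 − p)^27.

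| Assumed p | Expected uncounted of 27 | Chance of at least one |
|---|---|---|
| 2% | 0.54 | 42% |
| 5% | 1.35 | 75% |
| 10% | 2.70 | 94% |

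These are losses if 8.3.3 is applied as written on procedure day. If events are collected under 8.3.4 and then restricted to the SAP 3.5 window, the loss is zero.

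**Starting at consent.** With about two months before the procedure and 12 after, the pre-procedure stretch is 2/14 = 14% of the period. It includes the screening endoscopy and two weeks of omeprazole and sucralfate (protocol 1.3, 6.5). Events before randomization cannot depend on the arm. Counting them would not bias the difference, but it would add noise and pull a ratio towards one. That is why they belong outside the comparison.

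**The case against.** The case against is substantial. Section 8.3.3 itself also requires every on-study event to be documented whatever its cause, and asks about events at each visit. The schedule in protocol 1.3 assesses events on procedure day and at every follow-up visit, with no split by arm, and 8.2.18 agrees. Follow-up is by blinded staff (6.1.1, 6.3), who cannot apply an exposure rule without knowing the arm. SAP 1.0 gives the SAP precedence, and its window is arm-neutral. A coherent reading therefore exists: collect under 8.3.4, then count under SAP 3.5.

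Most of this stands, and it rules out three stronger readings.
- A reader might infer that the sham count will be zero by rule over 12 months, so that any excess in the embolization arm would be an artefact. The sentences just cited show that recording in both arms is intended, and blinded staff could not produce that result.
- A reader might infer that access-site or vessel injuries would vanish from the trial's reporting. SAP 3.7 tabulates procedural complications, and protocol 9.4.6 and 10.1.6 send device- and procedure-related complications to the FDA and the DSMB. What is at risk is their place in the by-arm count.
- A reader might infer that these counts are the sole safety look by arm. Endoscopy is an exploratory endpoint justified as a safety measure (protocol section 3), and the DSMB reviews safety data for each arm.

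What does not stand is that the conflict is already resolved. The specific start rule sits beside the general sentence in one section, and the SAP has no recording rule that overrides it. On procedure day an unblinded team member records the procedure details (6.3) and could apply the exposure rule.

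**Conclusion.** The point holds as a wrong rule with limited reach. Section 8.3.3 as written does not give the arms a common window for the designated 12-month and 30-day safety comparisons, and it conflicts with three other start points. The realistic consequence is inconsistent recording, mainly of procedure-day events. That means up to about 0.5 to 2.7 uncounted embolization-arm participants of 27 at assumed rates of 2% to 10%, and none if 8.3.4 and the SAP window are followed.

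This rests on reading the device as the bead, on randomization taking place on procedure day as protocol 1.3 and 6.1.1 describe, and on event rates that are assumed. SAP 5.4 names no safety test and SAP 5.9 says the trial is not powered on safety, so I attach no p-value.

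**What to change.** Replace the two sentences in protocol 8.3.3 with one rule. Record as adverse events all events from randomization on procedure day, just before the embolization or sham steps, to the 12-month visit, in both arms, whether or not the device was given. Record events from consent to randomization separately and keep them out of the by-arm comparison.

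Randomization is a better start than sedation, which under 6.1.1 comes before any arm is assigned.

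Align protocol 8.3.4, SAP 3.5 and SAP 5.4 with this window. For the 30-day outcome, use days after the procedure throughout, because protocol section 3 counts from embolization, which sham participants do not have. SAP 3.2 implies that the procedure is scheduled after randomization; bring it into line with protocol 6.1.1 so that the start point falls on procedure day.

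The cost is a few sentences in the protocol and SAP, plus a check that the eCRF does not send sham or pre-infusion events to history. Visits, tests and sample size (21 evaluable, 27 randomized per arm) do not change.
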